## 2.6.1 Description of pharmacodynamic variables

There are three types of biomarkers in the study:

- Biomarkers measured in bronchoscopy samples, assessed in biopsy, bronchoalveolar lavage fluid (BALF), and brushing at baseline and Week 12/EOT
  - Immunohistochemistry (IHC)/immunocytochemistry (ICC) markers.
  - Subepithelial thickness in biopsy samples.
  - Differential cell count in BALF samples.
  - RNA markers.
  - Proteins (in brushing and BALF samples).

Note: depending on feasibility, additional biomarkers might be analyzed.

- Biomarkers measured in blood assessed at baseline, Week 6 and 12/EOT (differential cell count, RNA markers, proteins).
- FeNO measured at baseline, Weeks 6, 8, 10 and 12/EOT.

The [Table 5](#) contains the comprehensive list of the bronchoscopy and blood biomarkers that will be assessed during the study.

The last value before the first IMP will be considered as baseline:

- For bronchoscopy parameters, the baseline is defined as the value at Visit 2 (screening).
- For blood biomarkers, the value at visit 2 is considered as baseline unless not available (eg, insufficient volume); in that case the baseline will be the value determined at Visit 1.
- For FeNO, the baseline is defined as the latest value prior to first dosing.

No imputation of missing values will be performed.

Rules for imputation of values below the LLOQ or above the upper limit of quantification (ULOQ) are detailed in [Section 2.11.2](#).

### 2.6.1.1 Main endpoints

The following inflammatory cells measured in biopsy samples by IHC will be considered as the main markers:

- Eosinophils, based on major basic protein (MBP) positive cells; the hypothesis is that dupilumab will decrease tissue eosinophils in patients with persistent asthma compared to placebo, as it was demonstrated in the R668-PH-17214 study that dupilumab potently blocked house dust mite-induced eosinophil infiltration into the lungs of *Il4rahu/hu Il4hu/hu* mice.
- Mast cells: tryptase positive, chymase positive.
- T lymphocytes: CD3 positive.

- T helper cells: CD4 positive.
- Goblet cells: MUC5 positive.
- B cells: CD23 positive.

The main endpoints will be the absolute change from baseline, the percent change from baseline as well as the ratio from baseline at Week 12/EOT for:

- The number of positive inflammatory cells per mm^2, derived by the biostatistics department, for each marker described above as:

$$\frac{\text{Number of positive inflammatory cells}}{\text{Total area of tissue assessed in mm}^2}$$

- For goblet cells (MUC5 positive) only, the following ratios will be also calculated by the biostatistics department:

- $\frac{\text{Total positive area assessed in mm}^2}{\text{Total area of tissue assessed in mm}^2}$
- $\frac{\text{Number of positive inflammatory cells}}{\text{Total positive area assessed in mm}^2}$

All IHC measurements will be assessed in triplicate; the mean of the 3 values will be used for all statistical analyses. Of note, the previous ratios will be calculated for each replicate first and then the 3 replicates will be averaged (the missing values will not be imputed and the average of the replicates will be calculated whatever the number of non missing values)

### **2.6.1.2 Exploratory endpoints**

#### **2.6.1.2.1 Markers measured by ICC**

The following inflammatory markers measured by ICC in BALF and brushing samples will be considered as exploratory markers:

- Eosinophils: MBP positive cells
- Mast cells: tryptase positive
- Macrophages: CD206 positive, CD68 positive
- B cells: CD23 positive

Exploratory endpoints will be the absolute change from baseline, the percent change from baseline as well as the ratio from baseline at Week 12/EOT for:

- BALF samples: The absolute number of stained cells for each marker described above, expressed in cells by mL of fluid and calculated by the biostatistics department:

$$\frac{\text{Absolute number of stained cells}}{\text{Total recovered volume in mL}}$$

- BALF and brushing samples: The following ratios will be also calculated by the biostatistics department for each cell type:
  - $\frac{\text{Absolute number of stained cells}}{\text{Total number of inflammatory cells}}$
  - $\frac{\text{Number of stained CD206 cells}}{\text{Number of stained CD68 cells}}$ , reflecting M2/M1 macrophages differentiation

#### 2.6.1.2.2 Subepithelial thickness markers

The subepithelial thickness measured in the biopsy will be considered as exploratory markers. The geometric mean of the thickness of basement membrane measured in 3 different locations will be computed by biostatistics department (of note, potential missing values will not be imputed and the average of the thickness will be calculated whatever the number of non-missing values).

Measurements will be assessed in duplicate; the geometric mean across the 3 locations will be calculated first and the arithmetic mean of the 2 replicates will be computed (the missing values will not be imputed and the average will be calculated whatever the number of non-missing values)

The absolute and percent change from baseline at Week 12/EOT for these markers will be considered as exploratory endpoints.

#### 2.6.1.2.3 Differential cell counts

The following markers will be considered as exploratory markers:

- Differential cell counts in BALF: neutrophil, eosinophil, lymphocyte, macrophage, epithelial, and mast cell counts
- Differential cell counts in blood: as part of the standard White Blood Cell differential cell count (see [Section 2.8.2](#)), total white blood cell count, neutrophils, eosinophils, basophils, monocytes and lymphocytes will be analyzed at baseline and Week 12/EOT.

The absolute change from baseline, the percent change from baseline as well as the ratio from baseline at Week 12/EOT for these markers will be considered as exploratory endpoints.

#### 2.6.1.2.4 RNA markers

The effect of dupilumab on the mRNA expression of 29 Th2-related genes (see the list of genes in [Appendix D](#)) after quantitative RT-qPCR will be explored. RNA will be isolated from bronchoscopy in biopsy, BALF and brushing samples at baseline and Week 12/EOT and also in blood at baseline only.

Prior to all statistical analyses, mRNA data will be normalized using a combination of the housekeeping genes B2M and GAPDH if  $C_t$  ranges ( $C_{tmax} - C_{tmin}$  among all study samples) of these 2 genes is  $<4$ . If so, the individual  $\Delta C_t$  will be calculated for each patient and visit as follows:  $\Delta C_t = C_{t,target} - C_{t0}$ , where:

$C_{t0}$  = arithmetic mean of  $C_{(t, 2 \text{ housekeeping genes})}$  for each biopsy specimen

For lung samples, the  $\Delta\Delta C_t$  between Week 12/EOT and baseline as well as fold-change from baseline in gene expression will be calculated for each patient as follows:

- $\Delta\Delta C_t = (C_{t,\text{target}} - C_{t0})_{(\text{Week 12})} - (C_{t,\text{target}} - C_{t0})_{(\text{Baseline})}$
- Fold-change,  $FC = 2^{-\Delta\Delta C_t}$

If  $C_t$  ranges of both housekeeping genes are  $\geq 4$ , alternative normalization algorithms, such as Quantile normalization, will be used.

Note: Please note that the statistical analyses for microarray RNA data (to be assessed from biopsy, BALF, and brushing samples at baseline and Week 12/EOT, and from blood sample at baseline only) will be described in a separate document.

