### 1.3 DETERMINATION OF SAMPLE SIZE

The sample size and the statistical power are estimated based on the pharmacodynamics (PD) endpoint of fractional exhaled nitric oxide (FeNO) as a surrogate marker for airway inflammation as no historical data was available on the main endpoints of bronchial inflammatory cells at the time of the protocol writing no historical data is available on the main endpoints of bronchial inflammatory cells.

The following assumptions are used for the estimations:

- A difference of 25 parts per billion (ppb) in the change from baseline in FeNO at Week 12/end of treatment (EOT) between dupilumab and placebo, and a common standard deviation (SD) of 32 ppb (this corresponds to a hypothesized effect size of 0.78)
- A t-test at 1-sided  $\alpha=0.05$
- Not accounting for early dropout, i.e., the calculated sample size refers to the number of completers who have baseline and Week 12/ EOT bronchoscopy measurements and have adequate biopsies (i.e., of sufficient quality, from which quantitative results are available for at least one of the biomarkers tested) for analysis at both baseline and Week 12/EOT.

Based on above assumptions, it is estimated that, with a total of 42 completers with adequate biopsy samples (21 completers per group), the study will have an 80% power to detect a difference of 25 ppb in the change from baseline in FeNO at Week 12/EOT between dupilumab and placebo.

Based on observations in other clinical trials (see Section 9.5 of the study protocol), it is expected that this sample size will be sufficient to evaluate the main PD endpoints in bronchial submucosa. Brightling et al (1) powered their study to show a reduction in airway submucosal eosinophils from baseline to Week 12 for their active drug compared with placebo using the following SD of the log values of the ratio vs. baseline in the change in number of eosinophils per mm^2 of subepithelial tissue in bronchial biopsy: 1.62 for the active group and 1.82 for placebo

Using an estimate of the SD of the log of the ratio in both groups of 1.7, it is calculated that 21 patients per group (planned sample size of the PDY14192 study) would be sufficient to detect a 3.8-fold decrease (corresponding to a hypothesized effect size of 0.78 in log of ratio) compared with placebo with 80% power (one-sided test at 5%).

[figure not shown]
The calculations were made using nQuery Advisor 7.0.

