### **Multiplicity issues**

In all statistical models performed, unadjusted (ie, nominal) p-values and p-values adjusted to control the false discovery rate (FDR) using the Benjamini-Hochberg procedure (2) at a 10% threshold will be systematically presented in all outputs.

The adjustment will be done separately for each of group of biomarkers:

- IHC markers in biopsy samples.
- ICC markers in BALF samples.
- ICC markers in brushing samples.
- Subepithelial thickness.
- Differential cell counts in BALF.
- Differential cell counts in blood.
- RNA markers in biopsy.
- RNA markers in BALF.
- RNA markers in brushing.
- Proteins in BALF.
- Proteins in brushing.
- Proteins in blood.
- FeNO.

All the p-values coming from the statistical analyses performed on the corresponding PD endpoints (for absolute change from baseline and ratio from baseline, for all types of markers within a group) will be taken into account for the multiplicity adjustment.

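### RNA markers: the housekeeping-gene check, read literally, pools all sample types, and the one fallback it names can distort effects in a small Th2 panel

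*SAP*

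**What the plan says.** Section 2.6.1.2.4 (RNA markers) of the SAP plans to explore "the mRNA expression of 29 Th2-related genes" by RT-qPCR. On the samples it says: "RNA will be isolated from bronchoscopy in biopsy, BALF and brushing samples at baseline and Week 12/EOT and also in blood at baseline only".

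The default is delta-Ct against the arithmetic mean of two housekeeping genes: "mRNA data will be normalized using a combination of the housekeeping genes B2M and GAPDH if" the Ct range of these genes is below 4. The range is maximum minus minimum Ct, taken "among all study samples". If the ranges of both genes are 4 or more, "alternative normalization algorithms, such as Quantile normalization, will be used".

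The section does not say what happens when one gene is below 4 and the other is not.

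Under Multiplicity issues (section 2.6.2.3), RNA results form separate false-discovery-rate families by lung matrix. The first is "RNA markers in biopsy", followed by BALF and brushing.

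**The concern.** There are three weaknesses in the one rule.

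- **Scope of the check.** The range is computed on raw Ct, so it includes the loading variation that normalization is meant to remove. A maximum-minus-minimum range also grows with the number of samples. If all matrices are pooled, ordinary differences in Ct level between tissue, lavage, brushings and blood add to it. The check can then reject housekeeping genes that are stable within each matrix, which is where the analysis is done.
- **Fallback.** Quantile normalization gives every sample the same distribution of values. That is harmless if few genes change or if changes cancel. It is risky for 29 genes selected from one pathway, because a net shift of the panel is treated as technical and removed.
- **Gap.** The one-gene-fails case is not covered, and the fallback algorithm is left open.

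At stake are the RNA results in biopsy, BALF and brushing. The error would be bias, not noise: smaller effects on genes that respond and apparent opposite changes in genes that do not. False-discovery-rate adjustment does not correct bias.

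**Working it through.** **The plan's own figures.** The SAP gives no power, Ct SD or between-matrix difference for the RNA panel, so there is no RNA figure to reproduce. The only figure used is the number of patients, from section 1.3: "with a total of 42 completers with adequate biopsy samples (21 completers per group), the study will have an 80% power". It reproduces: effect size 25/32 = 0.78, 21 per group, one-sided 5% t-test, power 80.05%. The point does not rest on it.

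**Step 1: samples in the range.** One lung matrix gives 42 × 2 visits = 84. Three lung matrices give 84 × 3 = 252. Adding baseline blood gives 252 + 42 = 294.

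**Step 2: how often one gene's range reaches 4.** Assumed: independent normal Ct values with no difference between matrices. Expected range = multiplier × SD, with simulated multipliers 4.9, 5.6 and 5.7.

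| Assumed Ct SD | 84 samples | 252 samples | 294 samples |
|---|---|---|---|
| 0.5 | <0.1% | <0.1% | <0.1% |
| 0.6 | 0.7% | 4.6% | 5.5% |
| 0.7 | 10% | 41% | 48% |
| 0.8 | 40% | 89% | 93% |
| 1.0 | 94% | 100% | 100% |

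These are chances for one gene, whereas the fallback needs both genes to fail. If the two move together, as with shared loading, the figures stand. If they were independent, the SD 0.7 row would be squared: 0.097² = 0.9%, 0.415² = 17%, 0.483² = 23%. The increase with pooling remains either way.

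**Step 3: differences between matrices.** Assumed within-matrix SD 0.5 and three lung matrices of 84 samples. One matrix alone reaches 4 in about 0.02% of cases or fewer. Pooled, the chance is 5% if the matrix means span 1 Ct, 94% if they span 2 Ct and about 100% if they span 3 Ct.

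**Step 4: what quantile normalization does.** Assumed: 21 per arm, two visits, 29 genes, k genes shifted by 1 Ct in the same direction on dupilumab, loading SD 1, noise SD 0.7, between-gene SD 2 to 4. The estimate is the arm difference in change.

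| Genes moved | Kept on moved genes (true 1.00) | False shift on unmoved genes |
|---|---|---|
| 3 | 0.69 to 0.79 | -0.08 to -0.09 |
| 10 | 0.51 to 0.57 | -0.27 to -0.30 |
| 15 | 0.37 to 0.41 | -0.40 to -0.44 |
| 20 | 0.24 to 0.27 | -0.53 to -0.59 |
| 29 | 0.00 | none left |

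Against a reference unaffected by treatment, delta-delta-Ct returned 0.97 to 1.03 on moved genes and about 0 on the rest.

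*Arithmetic check.* Every normalized sample has the same sum over genes, so k × kept + (29 - k) × false shift must be close to 0. At between-gene SD 3: for k = 10, 10 × 0.55 + 19 × (-0.29) = -0.01; for k = 20, 20 × 0.25 + 9 × (-0.55) = 0.05. Both agree within rounding.

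**Step 5: other directions.** With 10 genes up and 10 down by 1 Ct, 0.81 to 0.85 is kept and there is no false shift. With 7 down and 3 up, the larger group keeps 0.73 and unmoved genes shift by -0.12.

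**Step 6: limits of housekeeping methods.** If treatment itself moves the housekeeping genes by 0.5 Ct, delta-Ct gives 1.00 - 0.50 = 0.50 on moved genes and -0.50 on the rest. Using change in housekeeping Ct as a covariate gives 0.52 to 0.56 and -0.44 to -0.48 at loading SD 1.

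**The case against.** The strongest reply has four parts.

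- **Quantile normalization is only an example within a contingency.** This stands. A reader might infer that the SAP commits to it. The wording does not support that: the default is housekeeping delta-Ct, and the fallback is open. An open choice made after the Ct values are known is itself a weakness, but a smaller one.
- **The size depends on unsupported assumptions.** This stands in part. A reader might infer that the method would erase the treatment effect. That happens only if all 29 genes shift equally in one direction. The body of the SAP calls the genes Th2-related and says the effect will be explored; it does not say how many should move, which way or by how much. Steps 4 and 5 therefore give a range.
- **Pooling is one reading.** This stands. The housekeeping mean is defined per biopsy specimen and RNA is tested by matrix, so a per-matrix check may have been intended. The literal text says otherwise and should be settled.
- **Housekeeping methods can be biased too.** This stands, as step 6 shows. It means the alternative needs its own check. It does not make quantile normalization suitable for this panel.

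**Conclusion.** The point holds as a weakness in a contingency rule. Followed literally, the rule can discard housekeeping genes that are stable within each matrix and send the data to a method that attenuates a net directional effect and creates opposite shifts in unaffected genes. At an assumed Ct SD of 0.7, pooling raises the chance that one gene fails from about 10% to 41% or 48%. If quantile normalization were then used and the movement were one-directional, a 1 Ct effect would fall to about 0.5 to 0.6 with 10 movers and about 0.25 with 20. With balanced movement the loss is small.

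The Ct SDs, between-matrix differences, gene counts, direction and shift size are all assumptions. The harm requires the trigger to fire, quantile normalization to be chosen and the panel to move in a net direction. A reader might infer that the trial's main conclusion is at risk. The SAP does not support that: RNA markers are exploratory, and the main endpoints are inflammatory cells by immunohistochemistry, which this rule does not touch. The change is worth considering; it is not essential to the trial.

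**What to change.** Amend section 2.6.1.2.4 before unblinding as follows:

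1. Compute each housekeeping gene's Ct range within each matrix, not over all matrices.
2. In each matrix, use both genes if both ranges are below 4, and the stable one if only one is.
3. If neither is below 4 in a matrix, use one named fallback that does not rely on the panel genes' own distribution. One option is to model change in target Ct with change in housekeeping Ct as a covariate, after checking that housekeeping Ct change does not differ by arm. That check uses treatment allocation, so what follows from each result must also be written in advance.
4. State that quantile normalization will not be used for this panel.

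The cost is a few sentences and no new data. Single-gene normalization is slightly noisier. Any housekeeping-based method is biased if treatment moves the housekeeping genes, and a check in about 21 patients per arm may miss a modest shift, so the report should show the housekeeping Ct changes by arm. A per-matrix check can still fail. At SD 0.7, taking matrices as independent, the chance that one gene fails in at least one of three is 1 - (1 - 0.097)³ = 26%, but only the failing matrix would then go to the fallback.

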#### 2.6.1.2.5 Proteins

Following proteins will be measured:

- In brushing at baseline and Week 12/EOT: 15-LO1, GPX4, LC3, iNOS, DUOX2, FOXA3. The value of the protein expression will be background-subtracted and normalized to GAPDH by the vendor.
- In BALF at baseline and Week 12/EOT: Periostin, Eotaxin-3, MCP-4, TARC, and the following cytokines: IL-6, IFN- $\gamma$ , TNF- $\alpha$ .

Of note, blood urea nitrogen and BALF urea at the corresponding timepoints will be used to correct the protein levels by the dilution factor, i.e., the concentrations will be multiplied by the following factor:  $\frac{\text{BALF urea}}{\text{Blood urea nitrogen}}$  before analysis.

- In blood at baseline, Weeks 6 and 12/EOT: Periostin, Eotaxin-3, MCP-4, TARC, PARC, ECP, Total IgE and regional specific IgE panels (see [Appendix C](#) for the list of the regional specific IgE panels, assessed at Visit 2 and Week 12/EOT only) and the following cytokines: IL-4, IL-5, IL-6, IL-13, IFN- $\gamma$ , TNF- $\alpha$

The absolute and percent changes from baseline in concentration levels will be analyzed as exploratory endpoints.

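### The urea correction for BALF proteins is inverted: it applies the lavage dilution a second time instead of removing it

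*SAP*

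**What the plan says.** SAP section 2.6.1.2.5 lists the lavage proteins as "In BALF at baseline and Week 12/EOT: Periostin, Eotaxin-3, MCP-4, TARC, and the following cytokines" IL-6, IFN-γ and TNF-α, seven analytes in all. It then provides for a dilution correction. The inputs are "blood urea nitrogen and BALF urea at the corresponding timepoints", and these "will be used to correct the protein levels by the dilution factor, i.e., the concentrations will be multiplied by the following factor". The factor that follows has BALF urea in the numerator and blood urea nitrogen in the denominator. Of the protein values the section says: "The absolute and percent changes from baseline in concentration levels will be analyzed as exploratory endpoints".

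The BALF proteins are modelled under the exploratory PD analyses of section 2.6.2.3 and form their own false-discovery-rate group, "Proteins in BALF". No other section gives a different formula or says that concentrations are divided by the ratio.

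**The concern.** The purpose and the formula point in opposite directions. A lavage sample (4 x 50 mL instilled per visit, Table 5) is lining fluid diluted with instillate. BALF urea is therefore lower than blood urea, and the written ratio is below 1. Multiplying an already diluted concentration by a number below 1 lowers it further; a correction should raise it back to the lining-fluid level.

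Dilution varies from one bronchoscopy to the next, so the error stays in the change from baseline. A programmer who follows the text exactly would produce wrong values for every BALF protein. These values also enter the baseline correlations and clustering (section 2.6.2.4), the correlations with baseline characteristics (2.6.2.5), the correlations with changes in FEV1 and FeNO (2.6.2.6) and the predictive models (2.6.2.8).

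**Working it through.** **Premise.** Any urea correction assumes that urea has the same concentration in blood and lining fluid and is absent from the instilled fluid. The SAP does not state this, but without it there is no reason to use urea. Let D be the dilution, C the true protein level and U the urea level. Then measured protein = C/D and BALF urea = U/D.

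**Algebra.**
- SAP factor: (C/D) × (U/D)/U = C/D².
- Inverse factor: (C/D) × U/(U/D) = C.

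With C = 100 (assumed):

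| D | Uncorrected | SAP formula | Inverse |
|---|---|---|---|
| 20 | 5 | 0.25 | 100 |
| 50 | 2 | 0.04 | 100 |
| 100 | 1 | 0.01 | 100 |
| 200 | 0.5 | 0.0025 | 100 |

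**Percent change in one patient with no true change.** The result is D0/D1 − 1 uncorrected, (D0/D1)² − 1 under the SAP formula and 0 with the inverse. The dilutions are assumed.

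| D at baseline → Week 12 | Uncorrected | SAP formula | Inverse |
|---|---|---|---|
| 50 → 100 | −50% | −75% | 0% |
| 100 → 50 | +100% | +300% | 0% |
| 60 → 90 | −33.3% | −55.6% | 0% |

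**Variance of the log change.** Assume a true log-change SD of 0.8 (variance 0.64) and a log-dilution SD of s per visit, independent between visits and of the protein. The variance is 0.64 with a perfect correction, 0.64 + 2s² uncorrected and 0.64 + 2(2s)² = 0.64 + 8s² under the SAP formula.

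| s | Uncorrected | SAP formula | SAP / correct | SAP / uncorrected | Dilution share under SAP, 8s²/(0.64 + 8s²) |
|---|---|---|---|---|---|
| 0.2 | 0.72 | 0.96 | 1.5 | 1.3 | 33% |
| 0.3 | 0.82 | 1.36 | 2.1 | 1.7 | 53% |
| 0.5 | 1.14 | 2.64 | 4.1 | 2.3 | 76% |

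**Percent change, the scale the SAP plans.** If log dilution is normal and unrelated to treatment, the mean of (D0/D1)² is exp(8s²/2) = exp(4s²): 1.17, 1.43 and 2.72 for s = 0.2, 0.3 and 0.5. The mean ratio to baseline in each arm, and so the difference between arms in mean percent change, is multiplied by that amount. A null difference stays null, but a real one is reported too large and with more noise.

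**Power.** Assume a per-visit protein log SD of 0.5, so that the true SD of the log ratio is √(2 × 0.25) = 0.71. With s = 0.3 the SD is √(2 × (0.25 + 0.09)) = 0.82 uncorrected and √(2 × (0.25 + 0.36)) = 1.10 under the SAP formula. For a 2-fold effect with 21 patients per arm and a one-sided 5% t-test, power is 0.93 with the inverse factor, 0.85 uncorrected and 0.64 under the SAP formula.

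**Spurious correlation.** All BALF proteins from one sample share the same 1/D². For two independent proteins, each with log SD 0.5, and s = 0.3, the log-scale correlation is 0.36/(0.25 + 0.36) = 0.59 under the SAP formula, 0.09/(0.25 + 0.09) = 0.26 uncorrected and 0 with the inverse.

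**Bias.** If treatment shifts mean log dilution at Week 12 by δ, the between-arm difference in log protein shifts by −2δ under the SAP formula, −δ uncorrected and 0 with the inverse.

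**The case against.** The inversion is hard to dispute. Reading the ratio as a dilution factor works only if the concentration is divided by it, and the SAP says multiplied. The orientation of the printed fraction should be confirmed in the issued document, but nothing in the text suggests another reading. The stronger objections concern size and reach.

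- **Reach is limited.** The seven proteins are exploratory and make up one of 13 separately adjusted groups, so other groups' adjusted p-values are unaffected. The biopsy endpoints, FeNO, the efficacy models, safety and the sample size do not use the factor. This stands.
- **Noise rather than bias.** If dilution is unrelated to treatment, the comparison loses precision but is not biased under the null. This stands, except that a real difference in percent change is inflated as shown. The SAP gives no evidence that treatment alters dilution.
- **The size rests on assumptions.** The SDs are not in the SAP, the variance multiples are on the log scale while proteins are analysed as absolute and percent change, and the reference is a perfect correction without urea assay error. Against no correction the central multiple is 1.7, not 2.1. Nor does dilution dominate everywhere: its share is 33% at s = 0.2. All of this stands.
- **The −75% is one patient.** With s = 0.3 the between-visit SD of log dilution is √2 × 0.3 = 0.42, so a doubling (0.69) lies 1.6 SD out, about 1 patient in 20 in that direction. It shows the mechanism and is not a group effect.
- **Urea against urea nitrogen is minor.** On a mass basis the mismatch is a constant of about 2.14. It cancels in percent change and rescales absolute change without altering linear-model p-values. Section 2.8.2 also plans conversion of laboratory values to standard international units. It is still worth settling while the formula is being rewritten.

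None of these points makes the written formula right.

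**Conclusion.** The concern holds. As written, the correction turns C/D into C/D² and doubles the dilution error on the log scale, which is worse than no correction. The direction depends only on the premise that underlies any urea adjustment. The size depends on how much dilution varies between visits, which the SAP does not give: under the stated assumptions the variance of log change is 1.5 to 4.1 times that of a correct adjustment, and 1.3 to 2.3 times that of uncorrected data. The damage is confined to the seven exploratory BALF proteins, their false-discovery-rate group and the correlation, clustering and predictive analyses that use them. Within that family, results produced as specified could not be relied on.

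**What to change.** In section 2.6.1.2.5, replace the factor with blood urea divided by BALF urea at the same timepoint, or keep the ratio and state that concentrations are divided by it. State that both measurements are expressed as the same analyte in the same units, converting urea nitrogen to urea where needed. Correct the derivation program to match. A supportive table of uncorrected concentrations would be useful but is optional.

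The cost is one formula in the SAP and in its program, with no new data. It should be done before database lock; a later correction would be a post-hoc change to a pre-specified derivation.
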